2 SYNOPSIS

NAME OF SPONSOR: Amgen	PROTOCOL No.: 20130108			
NAME OF STUDY TREATMENT: ABP 798				
TITLE OF STUDY: A Randomized, Double-Blind Study to Compare Pharmacokinetics and Pharmacodynamics, Efficacy and Safety of ABP 798 with Rituximab in Subjects with Moderate to Severe Rheumatoid Arthritis				
STUDY CENTERS: Approximately 80 sites in Europe and North America	STUDY PERIOD: Approximately 300 subjects will be randomized in a 1:1:1 ratio to receive ABP 798 or rituximab (US) or rituximab (EU). The end of trial will be the date when the last subject has completed their last study assessment.	PHASE OF DEVELOPMENT: Phase 1/3		
PLANNED STUDY DATES: 29 April 2016 to 28 February 2018. The expected enrollment duration is 12 months, and each subject will participate for up to 52 weeks.				
OBJECTIVES: Primary Objective: The primary objective for this study is to demonstrate pharmacokinetic (PK) similarity (as assessed principally by area under the serum concentration-time curve [AUC] from time 0 extrapolated to infinity [AUC _{inf}] and the maximum observed serum concentration [C _{max}] following the 2 nd infusion of 1 st dose) of ABP 798 following 2 intravenous (IV) infusions of 1000 mg each, relative to that of 2 IV infusions of 1000 mg each of rituximab (US) and of rituximab (EU). Secondary Objective(s): The secondary objectives are 
to demonstrate PK similarity between rituximab (US) and rituximab (EU) as assessed by AUC_{inf} and by C_{max} after second infusion of the first doseto assess the clinical efficacy of ABP 798 compared with rituximabto assess the safety and immunogenicity of ABP 798 compared with rituximab.				
STUDY DESIGN AND METHODOLOGY: This is a randomized, double-blind, active-controlled 3-arm study in adult subjects with moderate to severe rheumatoid arthritis (RA) who have had an inadequate response or intolerance to other disease-modifying anti-rheumatic drugs (DMARDs), which must include intolerance or inadequate response to one or more tumor necrosis factor (TNF) inhibitor therapies. Approximately 300 subjects (100 per treatment group) will be enrolled. The subjects will be randomized to receive either ABP 798 1000 mg x 2 (treatment group A) infusions given 2 weeks apart, or rituximab (US) (treatment group B), or rituximab (EU) (treatment group C) 1000 mg x 2, given 2 weeks apart in a double-blinded fashion. Randomization will be stratified by geographic region, seropositivity (rheumatoid factor [RF]-positive and/or cyclic citrullinated peptide [CCP]-positive vs. RF-negative, and CCP-negative), and number of prior biologic therapies used for RA (1 vs. > 1). An independent data monitoring committee (DMC) will evaluate the safety data throughout the study, including an initial safety analysis after the first 18 subjects have received the first dose (1000 mg x 2 infusions of either ABP 798 or rituximab [EU] or rituximab [US]). At week 24, the subjects in treatment groups A and C will continue with and receive the second dose of the same treatment, and the subjects in treatment group B will transition to treatment group A1 and receive ABP 798 1000 mg x 2 as their second dose. Retreatment may occur earlier, ie, anytime from week 16 to week 24, in individual subjects, if necessary in the opinion of the Investigator. The end of study (EOS) will be at week 48 (or 24 weeks after the first infusion of the second dose for subjects retreated before week 24), and a final analysis will be performed when all subjects have completed or have had the opportunity to complete the week 48/EOS assessments.				
STUDY POPULATION AND MAIN CRITERIA FOR INCLUSION/EXCLUSION: Subjects cannot be randomized before all inclusion criteria (including test results) are confirmed.				

Inclusion Criteria:

1. Subjects must sign an Institutional Review Board (IRB)/Independent Ethics Committee (IEC)-approved informed consent form before any study specific procedures are preformed
2. Men or women ≥ 18 and ≤ 80 years old
3. Subjects must be diagnosed with RA as determined by meeting 2010 American College of Rheumatology (ACR)/European League Against Rheumatism (EULAR) classification criteria for RA
4. Duration of RA of at least 6 months
5. Active RA defined as ≥ 6 swollen joints and ≥ 6 tender joints (based on 66/68 joint count excluding distal interphalangeal joints) at screening and baseline and at least one of the following at screening:
 - erythrocyte sedimentation rate (ESR) ≥ 28 mm/hr
 - serum C-reactive protein (CRP) > 1.0 mg/dL
6. Subjects have had an inadequate response or intolerance to other DMARDs (which must include intolerance or inadequate response to one or more TNF inhibitor therapies)
7. Subjects must be taking methotrexate (MTX) for ≥ 12 consecutive weeks and be on a stable dose of MTX 7.5 to 25 mg/week for ≥ 8 weeks prior to receiving the investigational product (IP), and be willing to remain on a stable dose throughout the study
8. Subjects on non-steroidal anti-inflammatory drugs (NSAIDs) or low potency analgesics such as tramadol, soma compounds, fioricet, fiorinal, should be on stable doses for ≥ 2 weeks prior to screening
9. Subjects on oral corticosteroids, (≤ 10 mg prednisone or equivalent), should be on stable doses for ≥ 4 weeks prior to screening
10. Subject has no known history of active tuberculosis
11. Subject has a negative test for tuberculosis during screening defined as either:
 - negative purified protein derivative (PPD) < 5 mm of induration at 48 to 72 hours after test is placed)OR
 - negative Quantiferon test
12. Subjects with a positive PPD and a history of Bacillus Calmette-Guérin vaccination are allowed with a negative Quantiferon test
13. Subjects with a positive PPD test (without a history of Bacillus Calmette-Guérin vaccination) or subjects with a positive or indeterminate Quantiferon test are allowed if they have all of the following:
 - no symptoms per tuberculosis worksheet provided by the Sponsor, Amgen
 - documented history of treatment with a TB prophylaxis regimen, with at least 4 weeks of prophylaxis therapy completed at the time of screening. If a subject has completed at least 4 weeks of prophylaxis therapy, and their regimen requires >4 weeks therapy, the subject must be deemed able and willing to complete the entire prophylaxis regimen in accordance with local guidance
 - no known exposure to a case of active tuberculosis after most recent prophylaxis
 - no evidence of active tuberculosis on chest radiograph within 3 months prior to the first dose of IP

Exclusion Criteria:

Rheumatoid arthritis related

1. Class IV RA ([Hochberg et al, 1992](#)) according to ACR revised response criteria
2. Felty's syndrome (RA, splenomegaly, and granulocytopenia)
3. History of prosthetic or native joint infection

Other medical conditions

4. Planned surgical intervention during the duration of the study
5. Active infection or history of infections as follows:

- any active infection for which systemic anti-infectives were used within 4 weeks prior to first dose of IP
- a serious infection, defined as requiring hospitalization or IV anti-infectives within 8 weeks prior to the first dose of IP
- recurrent or chronic infections or other active infection that, in the opinion of the Investigator, might cause this study to be detrimental to the subject

6. Known history of human immunodeficiency virus
7. Hepatitis B surface antigen (HbsAg) or Hepatitis B core antibody (anti-HBc) positivity at screening (unless documentation of hepatitis B virus immunization) or Hepatitis C virus (HCV) antibody positivity at screening
8. Uncontrolled, clinically significant systemic disease such as diabetes mellitus, cardiovascular disease including severe heart failure (New York Heart Association [NYHA] class IV), or severe uncontrolled cardiac disease, renal disease, or liver disease
9. Malignancy within 5 years EXCEPT treated and considered cured cutaneous squamous or basal cell carcinoma, in situ cervical cancer, OR in situ breast ductal carcinoma
10. History of neurologic symptoms suggestive of central nervous system demyelinating disease
11. Major chronic inflammatory disease or connective tissue disease other than RA, with the exception of secondary Sjögren's syndrome
12. Concurrent medical condition that, in the opinion of the Investigator, could cause this study to be detrimental to the subject

Laboratory abnormalities

13. Laboratory abnormalities at screening, including any of the following:
 - hemoglobin < 9 g/dL
 - platelet count < 100,000/mm³
 - white blood cell count < 3,000 cells/mm³
 - aspartate aminotransferase (AST) and/or alanine aminotransferase (ALT) $\geq 2.0 \times$ the upper limit of normal
 - creatinine clearance < 50 mL/min (Cockcroft-Gault formula)
 - any other laboratory abnormality, which, in the opinion of the Investigator, will prevent the subject from completing the study or will interfere with the interpretation of the study results

Washouts and non-permitted drugs

14. Any of the following within 28 days prior to first dose of IP:
 - intra-articular (IA) hyaluronic acid injections
 - IA, intramuscular (IM), or IV corticosteroids, including adrenocorticotropic hormone
15. Non-biologic DMARDs, including Janus kinase inhibitors such as tofacitinib, other than MTX within 28 days prior to first dose of IP, except as below:
 - leflunomide (unless an active washout with cholestyramine has been performed), cyclosporine, azathioprine, tacrolimus excluded within 3 months prior to first dose of IP
 - use of IM or oral gold excluded within 6 months prior to first dose of IP
 - cytotoxic agents such as cyclophosphamide, D-penicillamine excluded within 6 months prior to first dose of IP
 - received IV gamma-globulin or Proscar column therapy excluded within 3 months prior to first dose of IP
16. Use of commercially available or investigational biologic therapies for RA as follows:
 - anakinra, etanercept within 1 month prior to first dose of IP
 - infliximab, abatacept, tocilizumab, golimumab, certolizumab, adalimumab within 3 months prior to first dose of IP
 - other experimental or commercially available biologic therapies for RA within 3 months or 5 half-lives (whichever is longer) prior to first dose of IP
17. Live vaccines within 28 days prior to the first dose of IP

	
18. Chronic use of high potency narcotic analgesics such as morphine or morphine derived medications, fentanyl, codeine, hydromorphone, levorphanol, meperidine, methadone, oxycodone or hydrocodone at screening19. Previous receipt of rituximab, a biosimilar of rituximab, or ocrelizumab20. Currently is enrolled in or has not yet completed at least 30 days or 5 half-lives (whichever is longer) since ending other investigational device or investigational drug, including vaccines, or subject is receiving other investigational agent(s)
General	
21. For women: pregnant or breast feeding, or planning to become pregnant while enrolled in the study and for 12 months after the last dose of IP22. Sexually active subjects and their partners who are of childbearing potential (ie, neither surgically sterile nor postmenopausal) and not agreeing to use adequate contraception (eg, true abstinence, sterilization, birth control pills, Depo-Provera injections, or contraceptive implants) while on study and for 12 months after the last dose of investigational product.23. Known sensitivity to mammalian cell derived drug products or hypersensitivity to the active substance or to any of the excipients of ABP 798 or rituximab24. Any physical or psychiatric disorder which, in the opinion of the Investigator, will prevent the subject from completing the study or interfere with the interpretation of the study results25. Any disorder that compromises the ability of the subject to give written informed consent and/or to comply with study procedures26. Active substance abuse, in the opinion of the Investigator (within 24 weeks of screening)
NUMBER OF SUBJECTS:	Approximately 300 subjects will be randomized in a 1:1:1 ratio to receive ABP 798, rituximab (US), or rituximab (EU), stratified by geographic region, seropositivity (RF-positive and/or CCP-positive vs. RF-negative and CCP-negative) and number of prior biologic therapies used for RA (1 vs. > 1). The sample size will provide > 90% power to demonstrate similarity on the primary PK endpoints, based on an assumption of between-subject variability (as measured by coefficient of variation) of 40%, true geometric mean ratio (GMR) of 1 among ABP 798, rituximab (US), or rituximab (EU), a margin of (0.8, 1.25), and 15% dropout by week 24. The PK similarity will be tested between ABP 798 versus rituximab (US) and ABP 798 versus rituximab (EU), each with a significance level of 0.05. The similarity between rituximab (US) and rituximab (EU) will be evaluated as well.
STUDY TREATMENT(S):	
Test Product, Dose and Mode of Administration:	ABP 798 (Treatment A) 500 mg/mL given at 1000 mg IV x 2 infusions 2 weeks apart
Reference Therapy, Dose and Mode of Administration:	Rituximab (US) (Treatment B) or rituximab (EU) (Treatment C) 500 mg/mL given at 1000 mg IV x 2 infusions 2 weeks apart
DURATION OF TREATMENT:	Subjects will receive a first dose (2 infusions at days 1 and 15), followed by a second dose (2 infusions 2 weeks apart beginning at week 24 or earlier, ie, anytime from week 16 to week 24, in individual subjects, if necessary in the opinion of the Investigator), with assessment until week 48 (or 24 weeks after the first infusion of the second dose for subjects retreated before week 24), plus a screening period of up to 4 weeks, for a total of up to 52 weeks. A total of 2 doses will be administered during the study; each dose will consist of 2 infusions, 2 weeks apart.
STUDY EVALUATIONS:	
Primary Criteria:	
• AUC_{inf}, C_{max} following the second infusion of the first dose
Secondary Criteria:	
• Percent of subjects with complete depletion in CD19+ cell count from day 1 to day 3• Disease Activity Score (DAS)28-CRP change from baseline at week 24• ACR20, ACR50 and ACR70• AUC from time 0 on day 1 prior to the first infusion of the first dose to 14 days postdose (day 15) (AUC_{0-14 day}), AUC from time 0 to week 12 (AUC_{0-12 wk}), C_{max} following the first infusion of the first dose

Safety Criteria:

- Treatment-emergent adverse events (AEs) and serious adverse events (SAEs)
- Clinically significant changes in laboratory values and vital signs
- Incidence of antidrug antibodies

STATISTICAL METHODS:

The PK similarity will be demonstrated by comparing the 90% confidence interval (CI) for the GMR of test (ABP 798)-to-reference (rituximab [US] or rituximab [EU]) **and rituximab [US] to rituximab [EU]** for AUC_{inf} and C_{max} following the second infusion of the first dose with the bounds of 0.8 to 1.25, where $\alpha=0.05$. PK parameters will be calculated using non-compartmental methods. Point estimates and CIs for the GMR will be estimated from an analysis of covariance model using the PK Analysis Set, consisting of all randomized subjects with an evaluable serum concentration-time profile.

Clinical equivalence will be evaluated for DAS28-CRP at week 24 using the Full Analysis Set consisting of all randomized subjects. **If PK similarity is established between rituximab (US) and rituximab (EU), the 2 arms will be combined into a single reference arm for the primary assessment of clinical equivalence between ABP 798 and rituximab. The results for ABP 798 vs. rituximab (EU) and ABP 798 vs. rituximab (US) will be provided for descriptive purposes. If PK similarity is not established, the ABP 798 arm will be compared to each of the individual rituximab arms separately to establish clinical equivalence of ABP 798 to the individual reference arms.**

With the planned sample size, there is **94% probability that the 90% CI of the difference between the ABP 798 arm and the pooled rituximab (rituximab[EU] and rituximab[US]) arm and 83% probability that the 90% CI of the difference between test (ABP 798) and reference (US-licensed rituximab or EU-authorized rituximab) in DAS28-CRP change from baseline at week 24 will fall into the equivalence margin of ± 0.6 (EULAR response criteria), assuming a standard deviation of 1.4 (Volkmann et al, 2010).** **DAS28-CRP at other timepoints and ACR20, 50 and 70 will be summarized descriptively.**

In addition, all categorical variables will be summarized using the number and percent of subjects falling into each category and all continuous variables will be summarized using mean, standard error or standard deviation, median, minimum, maximum, and number of subjects. Safety endpoints will be summarized descriptively as well, based on all randomized subjects who received at least one infusion of IP (ie, Safety Analysis Set).

DATE AND VERSION: 20 March 2018; Version 4.0

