8 INVESTIGATIONAL PLAN

8.1 Overall Study Design and Plan

[figure not shown]
This is a randomized, double-blind, active-controlled 3-arm study in adult subjects with moderate to severe RA who have had an inadequate response or intolerance to other disease-modifying anti-rheumatic drugs (DMARDs) (which must include intolerance or inadequate response to one or more TNF inhibitor therapies). Approximately 300 subjects (100 per treatment group) will be enrolled. The subjects will be randomized to receive either 2 IV infusions of ABP 798, 1000 mg each, given 2 weeks apart (treatment group A), or 2 IV infusions of rituximab (US) 1000 mg each, given 2 weeks apart (treatment group B) or 2 IV infusions of rituximab (EU), 1000 mg each, given 2 weeks apart (treatment group C), in a double-blinded fashion. A total of 2 doses will be administered during the study; each dose consists of 2 infusions, 2 weeks apart.

An independent data monitoring committee (DMC) will evaluate the safety data throughout the study, including an initial safety analysis after the first 18 subjects have been dosed (1000 mg x 2 infusions of either ABP 798 or rituximab [EU] or rituximab [US]).

At week 24, the subjects in treatment groups A and C will continue with and receive the second dose of the same treatment, and the subjects in treatment group B will transition to become treatment group A1 and receive the second dose with ABP 798. Retreatment may occur earlier, ie, anytime from week 16 to week 24 in individual subjects if necessary in the opinion of the Investigator.

The end of study (EOS) will be at week 48 (or 24 weeks after the first infusion of the second dose for subjects retreated before week 24), and a final analysis will be performed when all subjects have completed or have had the opportunity to complete the week 48/EOS assessments. [Figure 1](#) is a summary of the study design.

Figure 1. Study Diagram

* Retreatment will begin at week 24 or earlier, ie, anytime from week 16 to week 24 in individual subjects if necessary in the opinion of the Investigator.

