12.6.5 Pharmacodynamics

The PD similarity will be evaluated descriptively by calculating the 90% CI of complete CD19+ cell depletion rate difference between test-to-reference. The 95% CI will also be provided. The point estimate and CIs for rate difference will be estimated using a generalized linear model (specifically, a log-binomial regression model) with relevant baseline values and stratification factors as covariates using the FAS.

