## 3. STUDY DESIGN

This is a randomized, double-blind, active-controlled 3-arm study in adult subjects with moderate to severe Rheumatoid Arthritis (RA) who have an inadequate response or intolerance to other disease-modifying anti-rheumatic drugs (DMARDs), which must include intolerance or inadequate response to one or more tumor necrosis factor (TNF) inhibitor therapies.

Sponsor: Amgen Inc.

Statistical Analysis Plan

Protocol No: 20130108

10-December-2018/ Version 2.0

---

Approximately 300 subjects (100 per treatment group) will be enrolled. The subjects will be randomized to receive either 2 IV infusions of ABP 798, 1000 mg each, given 2 weeks apart (treatment group A), or 2 IV infusions of rituximab (US) 1000 mg each, given 2 weeks apart (treatment group B) or 2 IV infusions of rituximab (EU), 1000 mg each, given 2 weeks apart (treatment group C) in a double blind fashion. A total of 2 doses will be administered during the study; each dose consists of 2 infusions, 2 weeks apart.

An independent data monitoring committee (DMC) will evaluate the safety data throughout the study, including an initial safety analysis after the first 18 subjects have received the first dose (1000 mg x 2 infusions of either ABP 798 or rituximab (EU) or rituximab (US)).

At week 24, the subjects in treatment groups A and C will continue with and receive the second dose of the same treatment, and the subjects in treatment group B will transition to treatment group A1 and receive ABP 798 1000 mg x 2 as their second dose.

Retreatment may occur earlier, i.e., anytime from week 16 to week 24, in individual subjects, if necessary in the opinion of the Investigator.

The end of study (EOS) will be at week 48 (or 24 weeks after the first infusion of second dose for subjects retreated before week 24), and a final analysis will be performed when all subjects have completed or have had the opportunity to complete the week 48/EOS assessments.

See [Figure 1](#) below for a summary of the study design.

[figure not shown]

Sponsor: Amgen Inc.

Statistical Analysis Plan

Protocol No: 20130108

10-December-2018/ Version 2.0

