### 9.6.1 CD19

The pharmacodynamics similarity will be evaluated descriptively for the difference in percent of subjects with complete CD19+ cell depletion between test (ABP 798) and reference (US-licensed rituximab or EU-authorized rituximab) from day 1 to day 3. Subjects with baseline value less than 20 cell/uL or missing will not be evaluable for CD19+ depletion analyses. The point estimate, the 90% CI and the 95% CI will be provided for rate difference and will be estimated using a generalized linear model (specifically, a log-binomial regression model) with stratification factors as covariates. A sample SAS code for PROC GENMOD is displayed below:

CCI

Note: The contrasts in the estimate statement may need to be changed depending on the order of the treatments.

Descriptive statistics for CD19+ counts as well as change from baseline will be provided at day 2 and day 3.

In addition, for duration of CD19 complete depletion, KM estimates and 90% CIs will be calculated by randomized treatment group for event time quartiles.

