## 9.7 EFFICACY ANALYSES

All efficacy analysis will be performed using the FAS based on subject's randomized treatment. Sensitivity analysis of DAS28 at week 24 will also be performed using the per-protocol analysis set based on the actual treatment the subject received.

Analyses will be performed for two different time periods:

1. From day 1 until week 24 (efficacy analysis visit weeks 8, 12 and 24), only including results prior to 1st infusion of 2nd dose. Subjects who had the 1st infusion of 2nd dose prior to week 24 will have their efficacy endpoints data censored at the timing of 1st infusion of 2nd dose. For example, if disease

Sponsor: Amgen Inc.

Statistical Analysis Plan

Protocol No: 20130108

10-December-2018/ Version 2.0

---

assessment is done at day 1 of week 16 and 1st infusion of 2nd dose is done on the same day, then the disease assessment on day 1 of week 16 will be included in modeling, but any disease assessment after that day will not be included.

2. Day 1 through EOS (efficacy analysis visit weeks 8, 12, 24, 40 and 48). Analyses will be performed separately for all subjects and the subgroup of subjects who received the 1st infusion of the 2nd dose at week 24 (i.e., excluding early retreatment subjects as defined in [section 5.1](#)).

If PK similarity is established between rituximab (US) and rituximab (EU), the 2 arms will be combined into a single reference arm for the primary assessment of clinical equivalence of DAS28-CRP change from baseline at week 24 between ABP 798 and rituximab. The results for ABP 798 vs. rituximab (EU) and ABP 798 vs. rituximab (US) will be provided for descriptive purposes. If PK similarity is not established, the ABP 798 arm will be compared to each of the individual rituximab arms separately to establish clinical equivalence of ABP 798 to the individual reference arms.

The pooling of the reference arms for ACR20/50/70 and hybrid ACR analyses will be conducted similarly.

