### **9.8.1 Adverse Events**

All reported AEs will be coded to the appropriate SOC and PT according to the most current version of MedDRA, and the severity of each AE will be graded by the investigator per CTCAE v4.03 criteria.

Only TEAE will be tabulated.

Subject incidence of the following AEs will be tabulated by treatment groups and by SOC, PT, and maximum severity grade per CTCAE v4.03:

- treatment-emergent AEs

Subject incidence of the following AEs will be tabulated by treatment groups and by SOC and PT:

Sponsor: Amgen Inc.

Statistical Analysis Plan

Protocol No: 20130108

10-December-2018/ Version 2.0

- treatment-emergent AEs

Subject incidence of the following AEs will be tabulated by preferred term in descending order of frequency in the ABP798 column:

- treatment-emergent AEs
- grade 3 or higher treatment-emergent AEs
- treatment-emergent AEs leading to discontinuation of IP/study
- treatment-emergent AEs leading to infusion delay/infusion not given
- treatment-emergent AEOIs

For treatment-emergent AEOIs, the point estimate and 95% CI for RD of the subject incidence between ABP and the reference product are provided.

Exposure adjusted subject incidence rate (EAIR) of the following AEs will be tabulated by preferred term in descending order of frequency in the ABP798 column for the entire study:

- treatment-emergent AEs
- treatment-emergent AEOIs

The point estimate and 95% CI for RR of the EAIR between ABP and the reference product are also provided.

AEs leading to discontinuation of IP/study are those with an action taken with Investigational Medicinal Product of “dose discontinued” or those with other action taken of “discontinued from study”. If subjects have an AE for action taken with Investigational Medicinal Product of “dose delayed/not administered” checked, that AE leads to the infusion delay/infusion not given. If an AE leads to multiple actions taken with IP, only the last action will be captured in the eCRF.

Counting of AEs will be by subject, and subjects will be counted only once within each SOC or PT. For tables categorized by severity, subjects with multiple events within a particular SOC or preferred term will be counted under the category of their most severe event with that SOC or preferred term.

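### Once US–EU PK similarity is shown, the plan pools the rituximab arms for efficacy, including descriptive efficacy outputs, but not for CD19+ depletion; a supplementary pooled contrast would tighten that interval at almost no cost.

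*Protocol*

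**What the plan says.** **Where pooling applies.** The gate is US–EU PK similarity. If it is met, "the 2 arms will be combined into a single reference arm for the primary assessment of clinical equivalence between ABP 798 and rituximab" (Protocol Synopsis; repeated in 12.6.6). Protocol 12.6.6 also lists a pooled reference for the week 24 ACR20/50/70 intervals. SAP 9.7 adds: "The pooling of the reference arms for ACR20/50/70 and hybrid ACR analyses will be conducted similarly". SAP 9.7.2 and 9.7.3 call the ACR and hybrid ACR analyses descriptive.

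**CD19+ depletion.** Protocol 12.6.5 says: "The PD similarity will be evaluated descriptively by calculating the 90% CI of complete CD19+ cell depletion rate difference between test-to-reference". SAP 9.6.1 names the comparison as "between test (ABP 798) and reference (US-licensed rituximab or EU-authorized rituximab) from day 1 to day 3". Neither section mentions a pooled reference. In SAP Appendix 6, every output titled as pooled rituximab is an efficacy output, and CD19+ Table 14-11.2 has no pooled counterpart.

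**AEOIs.** SAP 9.8.1 says "the point estimate and 95% CI for RD of the subject incidence between ABP and the reference product are provided". It does not say whether the reference is US, EU or both combined.

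**The switch.** For the second dose, "the subjects in treatment group B will transition to treatment group A1 and receive ABP 798 1000 mg x 2 as their second dose" (SAP 3).

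**The concern.** The gate rests on exposure: AUC from time 0 extrapolated to infinity, and Cmax after the second infusion of the first dose. If similar exposure is enough to treat the two rituximab arms as one reference for a clinical score at week 24, the argument is at least as direct for B-cell depletion in the first three days. Depletion is a close pharmacological consequence of exposure and is measured long before any subject changes product.

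Descriptive status does not explain the difference, because the ACR and hybrid ACR analyses are descriptive too and still get a pooled contrast. What is at stake is the width of the interval for a listed secondary PD endpoint. For AEOIs the question is more basic: the trial has two reference products, and the text does not tell a programmer which one to use.

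**Working it through.** **1. The plan's own figures for the same pooling.** Inputs: "Approximately 300 subjects (100 per treatment group) will be enrolled" (Protocol 8.1); SD 1.4, true difference 0, margin ±0.6 and a 90% CI (SAP 3.1 and 9.7.1). Power = 2Φ(0.6/SE − 1.645) − 1, with SE = 1.4 × √(1/n₁ + 1/n₂).

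- 100 vs 100: SE = 0.1980; 0.6/SE = 3.030; power = 83.4% (stated 83%).
- 100 vs 200: SE = 0.1715; 0.6/SE = 3.499; power = 93.6% (stated 94%).

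Both reproduce with full arms and no dropout. The sponsor has therefore already quantified this pooling for DAS28-CRP.

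**2. Width ratio for a rate difference at equal rates.** The term p(1 − p) cancels:

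- separate: 1/100 + 1/100 = 0.020
- pooled: 1/100 + 1/200 = 0.015
- ratio of widths: √(0.020/0.015) = 1.155

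Each separate interval is 15.5% wider; equivalently, pooling cuts the standard error by 13.4%.

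**3. CD19+ half-widths.** The documents give no day 3 depletion rate, so a range is assumed. Unadjusted 90% half-width = 1.645 × √[p(1 − p)] × √(1/n₁ + 1/n₂), in percentage points:

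| Assumed rate | 100 vs 100 | 100 vs 200 |
|---|---|---|
| 70% | 10.7 | 9.2 |
| 80% | 9.3 | 8.1 |
| 85% | 8.3 | 7.2 |
| 90% | 7.0 | 6.0 |
| 95% | 5.1 | 4.4 |

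**4. Sensitivity.**

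- Evaluable numbers: "Subjects with baseline value less than 20 cell/uL or missing will not be evaluable for CD19+ depletion analyses" (SAP 9.6.1), so real arms may be smaller than 100. Equal proportional losses leave the ratio unchanged: 85 vs 85 against 85 vs 170 is again 1.155.
- Interval method: with Newcombe intervals the ratio is 1.15 to 1.18 for rates from 50% to 95%.
- Unequal rates: with ABP 798 at 90% and rituximab at 80% the ratio is 1.21; with those rates reversed it is 1.10.

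**5. AEOIs.** If the risk difference is in fact taken against one arm at a time, the same ratio applies in the first-dose period. At equal assumed incidences the 95% half-width is 6.0 vs 5.2 points at 5%, and 8.3 vs 7.2 points at 10%. That condition cannot be confirmed: SAP 9.8.1 leaves the comparator undefined, the Appendix 6 titles say only that results are by treatment, and the table shells are in a separate document.

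A 200-subject rituximab reference exists only up to the first infusion of the second dose. SAP 9.8 already defines that summary period, including for subjects retreated early.

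**The case against.** The strongest reply is that nothing here is wrong. Protocol and SAP agree on where pooling applies. It serves a decision rule for DAS28-CRP, whereas CD19+ depletion and safety have no margin, test or success criterion, so no conclusion turns on a half-width of 8.3 rather than 7.2 points. Separate contrasts also keep a US–EU difference visible. For adverse events, the plan makes no case that similar AUC and Cmax justify pooling.

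Most of this stands, and it makes the point a supplementary improvement. It does not explain why the descriptive ACR outputs are pooled and CD19+ is not. Visibility of a US–EU difference is preserved if the separate contrasts stay, and the same applies to AEOIs, where a pooled row would be read beside them.

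A reader might infer more: that AEOI comparisons are fixed at 100 vs 100, and that the plan therefore lowers the chance of seeing a real safety excess with ABP 798. The documents do not support either step. The first is inferred from table titles, because the text leaves the comparator open. The second holds only if one contrast is read alone. If both the US and the EU contrasts are shown, no rituximab data are discarded and a signal in either can be seen. The plan also sets no error-rate rule for AEOIs against which a detection probability could be judged.

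**Conclusion.** The point holds as a low-cost gain in precision. The SAP pools the rituximab arms for DAS28-CRP and for descriptive ACR and hybrid ACR outputs, but not for CD19+ complete depletion through day 3, and gives no reason. The separate CD19+ intervals are 15.5% wider than the pooled one, assuming equal rates and 100 evaluable subjects per arm (or equal proportional losses). The ratio runs from about 1.10 to 1.21 in the unequal-rate cases checked. The half-widths in points rest on assumed depletion rates and an unadjusted interval; the SAP's model adjusts for stratification factors.

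For AEOIs, the supported finding is that the comparator is undefined. Any pooled contrast there is valid only before the second dose. No decision rule in the trial changes.

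**What to change.** - **SAP 9.6.1 and Protocol 12.6.5:** state that, if US–EU PK similarity is established, ABP 798 is also compared with pooled rituximab for CD19+ complete depletion through day 3 (Table 14-11.2), as a supplement. Keep the separate US and EU contrasts.
- **SAP 9.8.1:** define the reference product for the AEOI risk difference. For the first-dose period only (Table 14-6.5.1.1), show the pooled contrast beside the US and EU contrasts, under the same gate.
- **Limit:** do not pool the rituximab arms for any period after the second dose begins, including the entire-study AEOI and exposure-adjusted comparisons.

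The cost is a few sentences and one more contrast in each of two tables. No new data, gate or margin is needed. The wording should be in place before unblinding so that the pooled contrast is not a post hoc choice.
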